Exclusion criteria:	
 1. Type 1 diabetes or diabetes clearly identified as having monogenetic etiology (e.g.: MODY). 2. Steroid-induced diabetes if steroid use is on-going or most recently taken within the last 3 months. 3. Pregnancy, plans to become pregnant within 6 months, or breast-feeding 4. Any use of insulin in the previous year. 5. Current or previous use of isCGM or rtCGM. 6. Cognitive dysfunction (SPMSQ score ≥ 5). 7. Symptoms of acute metabolic decompensation (extreme thirst, high urinary output, and weight loss, accompanied by acute fatigue or dyspnea). 8. Any terminal condition that would limit life expectancy to < 1 year. 9. Inability or refusal to use isCGM (e.g.: afraid of the device). 10. Inability or refusal to be reached by telephone. 11. Concurrent participation in another diabetes-related trial. 12. Has not already received two doses of a Health Canada-approved vaccine against SARS-CoV-2.
Evaluation criteria	
Primary Outcome: Change in glycated hemoglobin (HbA1c) at 3 months compared to baseline.
 
Secondary Outcomes: Feasibility of recruitment Blood pressure, body weight, waist circumference, and patient-reported outcomes, measured as change in continuous score at 3 months compared to baseline on validated instruments of:
 
 • Diabetes treatment satisfaction • Diabetes self-management empowerment • Diabetes-related distress • Diet • Physical activity

	Safety Outcomes: Any reported adverse events, major adverse events – hospitalization or ED visits. isCGM-related reactions (e.g.: skin reactions).
Treatment	Following informed consent, eligible adults will be randomly allocated to isCGM + education and feedback with a certified diabetes educator (CDE) or enhanced usual care with education and feedback using a 1:1 allocation ratio. The intervention (isCGM or enhanced usual care) will last 6-8 weeks. Those in the isCGM arm are free during the intervention or afterwards to obtain or fund their own supplemental isCGM sensors.
Randomization	Patients will be randomly assigned using a REDCAP based randomization system using variable block size. The computer-generated allocation table would be generated in a formal and secure manner.

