Sample size	A target sample of 100 patients was chosen based on funding constraints, power / sample size considerations, and expected loss to follow-up of 20-30%. The minimum number of trial completers required to have 80% power to detect an HbA1c difference of 0.5% is 80.
Follow-up	Follow-up (week 5-6) CDE virtual education and feed-back session. 12-week bloodwork encounter at outpatient lab. 12-week in-person study encounter to complete study measurements. After conclusion of the 12 week trial period: Post-trial qualitative interviews with select consenting participants. Post-trial administrative linkage to examine outcomes at 24-52 weeks from randomization – no direct participant involvement.

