14. STATISTICAL AND ANALYTICAL METHODS

Our sample size calculation was intended to detect an HbA1c difference of 0.5%, presuming a standard deviation of HbA1c values at 3 months of 0.78% based on a recent similar trial of capillary blood glucose monitoring. To have 80% power to detect this HbA1c difference at a type 1 error rate of 5%, we would need 40 trial-completers in each arm. Given expected loss-to-follow-up rates of 20% or more, our enrollment target will be 100 participants.

Data will be analyzed according to intention-to-treat principles. Patients will be kept in the study group to which they were randomized, and efforts will be taken to ascertain outcome events in all patients randomized. Discontinuation of study treatment (isCGM) or no-show to CDE encounters are not equivalent to withdrawal from the study, and efforts will be made to contact study participants for HbA1c measurements and patient-reported outcomes at 12 weeks regardless.

Outcomes (HbA1c and patient-reported outcomes) are continuous scores – the difference at 12 weeks from baseline will be presented using simple means and standard deviations. On change in HbA1c, our primary outcome, we will test for a difference between intervention and enhanced usual care arms using linear regression with adjustment for age and sex. Secondary outcomes and diabetes-related distress will be analyzed in similar fashion, including follow-up values for patient-reported outcomes obtained at 6 and 12 weeks. Safety outcomes are dichotomous (e.g.: ED visits), and differences between trial arms will be assessed using Fisher's exact test. The primary outcome will be considered statistically significant at $p < 0.05$. Secondary and safety outcomes are considered hypothesis-generating and will also be considered statistically significant at $p < 0.05$. No correction for multiple comparisons is planned *a priori*. If the primary outcome is statistically significant at $p < 0.05$, the Benjamini-Hochberg procedure will be performed on secondary outcomes targeting a false discover rate of 20%, if requested by reviewers.

Secondary analyses are planned, and include:

- Post-hoc analysis of outcomes in clinically relevant groups, e.g.: by sex, baseline self-management empowerment, etc., using the above methods.

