- Partitioning participants into those who improved their HbA1c by 0.5% or more, and examining predictors of improvement using logistic regression with simultaneous incorporation of other explanatory variables.

For the post-trial cohort study, the relationship between outcomes (HbA1c and health care utilization) and study allocation will be examined using linear (log-transformed or untransformed) and logistic regression models with simultaneous adjustment for multiple other variables, selected using a mixed purposeful / stepwise method.

For the qualitative sub-study, semi-structured interviews will be transcribed verbatim, anonymized, and will undergo thematic analysis using constant comparative methods. Co-investigators will interview transcripts independently and meet to develop a coding manual. The qualitative research associate will then code the remaining transcripts line by line. Team members will meet periodically to review and refine codes using a constant comparison method, with further sampling guided by emerging themes until content saturation is achieved.

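### Predictors of improvement are sought by cutting HbA1c change at 0.5%, which wastes power, and the plan leaves the role of baseline HbA1c open

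*Combined protocol and SAP*

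**What the plan says.** Section 14 describes the outcomes thus: "Outcomes (HbA1c and patient-reported outcomes) are continuous scores". The primary comparison is a linear regression of HbA1c change, adjusted for age and sex. Among the planned secondary analyses is "Partitioning participants into those who improved their HbA1c by 0.5% or more, and examining predictors of improvement using logistic regression", with other explanatory variables entered at the same time. The section does not list or count those variables. It does not say whether baseline HbA1c or study arm is among them, and it gives no continuous counterpart to this search for predictors.

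The trial is sized to "detect an HbA1c difference of 0.5%, presuming a standard deviation of HbA1c values at 3 months of 0.78" per cent, and Section 14 concludes that "we would need 40 trial-completers in each arm". The synopsis gives the same total ("The minimum number of trial completers required to have 80% power to detect an HbA1c difference of 0.5% is 80") and an "expected loss to follow-up of 20-30" per cent.

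**The concern.** Two separate things are at stake.

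The first is information. A person whose HbA1c falls by 0.5% is treated like one whose HbA1c falls by 2%, and unlike one whose HbA1c falls by 0.4%. In a sample this small, a real predictor of moderate strength may then be missed.

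The second is what counts as improvement. It is baseline minus follow-up, so any within-person variation in the baseline value enters the outcome directly. People who happen to start high tend to fall. Baseline HbA1c, or anything correlated with it, can then look like a predictor when nothing distinguishes those who benefit. This follows from the change score and is present with or without the cut.

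**Working it through.** **Inputs from the documents.** Difference 0.5%; SD 0.78% for HbA1c values at 3 months; 80% power at 5% type 1 error; 40 completers per arm, allocated "using a 1:1 allocation ratio"; 100 enrolled; 20-30% loss; improvement cut at 0.5%.

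**Assumptions not in the documents.** Normally distributed change; two-sided testing; a predictor correlated 0.3 with change; mean change of -0.1 to -0.5%; SD of change 0.78%; baseline to week-12 correlation ρ from 0.4 to 0.9, with equal SDs at both times. The plan's 0.78% is not an SD of change. With equal SDs, SD of change = 0.78 × √(2(1-ρ)), which equals 0.78% only at ρ = 0.5. It is 0.85% at ρ = 0.4 and 0.60% at ρ = 0.7.

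**1. The plan's own figure.** n per arm = 2 × (1.96 + 0.84)² × (0.78/0.5)² = 2 × 7.85 × 2.43 = 38.2, so 39. The t-test version gives 39.2, so 40, with 80.8% power at 40. The stated 40 per arm is reproduced. Of 100 enrolled, 20-30% loss leaves 80 to 70.

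**2. Responder rates.** Rate = Φ((-0.5 - mean change)/0.78). Mean changes of -0.5, -0.3 and -0.1% give 50%, 40% and 30%.

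**3. Power with the outcome kept continuous.** By Fisher's z, atanh(0.3) × √(80-3) = 0.3095 × 8.775 = 2.716, and power = Φ(2.716 - 1.96) = 78%. Simulation gives 76-81%.

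**4. Power after the cut.** The relative efficiency of a dichotomised normal outcome is φ(k)²/[p(1-p)], where p is the responder rate and k = Φ⁻¹(p). This is 0.637 at p = 0.5 and 0.576 at p = 0.3.
- p = 0.5: 2.716 × √0.637 = 2.167, power Φ(0.207) = 58%.
- p = 0.3: 2.716 × √0.576 = 2.061, power Φ(0.101) = 54%.

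Simulated logistic regression gives 51-57%. With the correlation fixed at 0.3, the SD of change matters only through the responder rate.

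With 70 completers, z = 0.3095 × √67 = 2.534. Power is then Φ(0.574) = 72% continuous. After the cut it is Φ(2.534 × 0.798 - 1.96) = 52% at p = 0.5 and Φ(2.534 × 0.759 - 1.96) = 48% at p = 0.3.

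**5. The same loss for a two-group contrast.** For a 0.5% difference between two groups of 40, with the lower-responding group changing by 0 to -0.75%:

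| SD of change | Continuous | After the cut |
|---|---|---|
| 0.6% | 96% | 72-84% |
| 0.78% | 81% | 55-62% |
| 1.0% | 60% | 39-42% |

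At 0.78%, restoring 80% power after the cut needs 61-72 per group against 39, or 1.6-1.8 times as many.

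**6. Baseline HbA1c as an artefactual predictor.** If week-12 HbA1c depends on nothing but baseline level, noise and a shift common to all participants, the correlation of baseline with change is -√((1-ρ)/2). That is -0.55 at ρ = 0.4, -0.39 at 0.7, -0.32 at 0.8 and -0.22 at 0.9. With 80 people and the 0.5% cut, baseline HbA1c reaches p < 0.05 in about 73-99% of simulated trials for ρ = 0.4-0.7, 48-60% at 0.8 and 22-37% at 0.9.

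**7. Null markers when baseline is omitted.** A marker correlated 0.4 with baseline and otherwise unrelated to outcome is significant in 13% (ρ = 0.8) to 28% (ρ = 0.5) of simulated logistic analyses. With baseline in the model the rate is about 3-6%.

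**8. Is the cut the cause?** For the uncut change score without baseline, the same marker's correlation with change is 0.4 × 0.5 = 0.20 at ρ = 0.5. Fisher's z gives 0.203 × 8.775 = 1.779, and Φ(1.779 - 1.96) = 43%. At ρ = 0.8 it is 0.4 × 0.316 = 0.126, z = 1.116, and Φ(1.116 - 1.96) = 20%. The artefact is at least as strong without the cut, so removing the cut alone would not cure it.

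**The case against.** The strongest defence is about reach. This is a secondary analysis with no power claim, in a plan that calls its secondary outcomes hypothesis-generating. The 0.5% cut equals the trial's own target difference, so it is not arbitrary. The preceding bullet plans analyses by sex, baseline empowerment and similar groups using the main methods, so some continuous analysis across patient groups is already there. All of this stands, and it limits the importance of the point. It does not recover the information lost in the predictor search itself.

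A reader might also infer more than the documents support:

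- **That the cut creates regression to the mean.** Step 8 shows otherwise.
- **That the model will be overloaded.** The plan gives no number of predictors. With SD of change 0.78%, the smaller outcome group would hold about 22-40 of 80 people, or 2-4 parameters at an assumed 10 per parameter. That is a limit to respect, not a demonstrated breach.
- **That baseline HbA1c is bound to be reported as a predictor.** The plan neither includes nor excludes it. If it is entered, the other predictors are adjusted for it and the artefact is confined to its own coefficient. How often it appears depends on a correlation that no document gives.
- **That the analysis sets out to show who benefits from isCGM.** The text asks for predictors of improvement, which is a different question from a difference in treatment effect.

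**Conclusion.** The point holds as a modest improvement to a secondary analysis. The loss of power from the cut appears in every scenario tried. For a predictor correlated 0.3 with change and 80 completers, power is about 76-81% continuous against 51-57% after the cut. These figures rest on an assumed correlation, normal change and responder rates of 30-50%.

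The baseline problem is separate and conditional. If baseline HbA1c is entered, its coefficient is artefactually significant well above 5% of the time across assumed correlations of 0.4 to 0.9, though the rate falls steeply as the correlation rises. If it is omitted, null markers related to it are over-flagged. Either way the plan should say how baseline is handled.

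Nothing here touches the continuous primary outcome or the 40 completers per arm, which reproduce.

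**What to change.** Replace the logistic model with a linear regression of 12-week HbA1c on the candidate predictors, with baseline HbA1c and study arm always in the model. State that the baseline coefficient will not be interpreted as a predictor of benefit. Report the share improving by 0.5% or more in each arm descriptively. Both parts are needed: a continuous outcome restores the power, and baseline in the model removes the over-flagging of related markers.

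Label any predictor-by-arm interaction exploratory. With 40 per arm, a slope difference of 0.3 SD has a standard error of about √(1/40 + 1/40) = 0.224, so power is Φ(0.3/0.224 - 1.96), or about 27%.

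The cost is a sentence or two in Section 14 and no new data, since HbA1c is already collected at baseline and 12 weeks. The downside is a less simple responder message.

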4. STUDY OBJECTIVES

Primary Objective

To evaluate the effectiveness of isCGM with CDE education and feedback on glycemic control at 12 weeks, in adults with type 2 diabetes and uncontrolled HbAc ($> 7.0\%$) not on insulin therapy.

Secondary Objectives

To determine the feasibility of recruiting adults with diabetes in Edmonton-area to a trial of glucose self-monitoring and education.

To determine the effectiveness of isCGM with CDE education and feedback on patient self-management of diabetes, measured using patient reported instruments for diabetes-related quality of life, diabetes treatment satisfaction, diabetes self-management empowerment, diet, and physical activity – at 6 weeks and at 12 weeks.

To determine the safety of isCGM with CDE education and feedback with respect to emergency department visits or hospitalizations, and isCGM-specific reactions (e.g.: skin reactions).

To understand the reasons *why* or *how* isCGM with CDE education is effective or ineffective from the perspective of involved participants and their providers.

To evaluate the effectiveness of isCGM with CDE education and feedback on glycemic control at 24-52 weeks (post-trial observational follow-up).

5. isCGM (INTERMITTENTLY SCANNED CONTINUOUS GLUCOSE MONITOR) – DESCRIPTION OF TECHNOLOGY

Technology – The only isCGM on the market at this time is the FreeStyle Libre 2 system produced by Abbott. FreeStyle Libre 2 sensors use a subcutaneous, wired enzyme glucose-

sensing technology, factory-calibrated to detect glucose levels in *interstitial* fluid by way of a thin filament implanted under the skin. The sensors are water-proof, affix to the skin by medical adhesive, last 14 days each, and are roughly the size of two stacked quarters. They measure interstitial glucose every minute, with readings stored in 15-minute intervals. Patients can scan sensors on-demand, using either a near-field communication-enabled smart phone or the FreeStyle Libre 2 Reader, to receive a glucose result along with historic results for the preceding 8 hours. The FreeStyle Libre 2 system is fully marketed in Canada; in 2020, it's predecessor, the similar FreeStyle Libre flash glucose monitoring system, had over 2 million users internationally.³²

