24-52 Week Post-Trial Observational Follow-up: After the trial ends, we will send out reminder letter to all participants and their providers encouraging them to have routine diabetes assessments, including laboratory measures, done. We will ascertain the effect of the intervention on HbA1c at 24 and 52 weeks, by review of NetCare. NetCare data up to 64 weeks post-randomization may be reviewed to assign the nearest lab value to the 52 week time point.

Other Quantitative Variables Measured:

Case report forms are provided in Appendix 5.

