- *Limited trial period of 12 weeks.* There is the possibility that insufficient time may have elapsed by the 12 week study HbA1c to see the effect of the intervention, since the 12 week HbA1c may be influenced by blood glucose exposure early in the trial period, before isCGM-based changes are made. Additionally, the 12 month outcome will not be able to speak to the sustainability of any isCGM benefits detected. We have designed a post-trial observational follow-up to address the longer term outcomes of episodic isCGM, recognizing that the follow analysis will no longer benefit from the expected confounder balance of randomization, as participants who consent to data linkage and who have HbA1c measurements post-trial will represent a non-random subset of those initially randomized.
- *Limited support to titrate anti-hyperglycemic medications.* The presumptive mechanism for any improvement in glycemic control is improved diet and lifestyle modification in adults randomized to isCGM. An alternative mechanism may be more rapid medication titration based on isCGM data, instead of HbA1c measurements, which are recommended at intervals no less than 90 days. While the

CDE algorithm (currently under development) may have a role for CDE-to-provider suggestions for medication changes, the intervention is not intended to provide further support or practice change related to provider prescribing (e.g.: decision support, alternate prescribers, provider training).

- *Sample size still has a 20% risk of type 2 error* – Our study is powered to detect a 0.5% difference in HbA1c at a power of 80%. The type 2 error rate (failure to detect a difference on such a difference truly exists) is still 20%, though may be slightly lower if loss-to-follow-up is minimized and recruitment approaches the full 100 participants.

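### The 24-52 week comparison of arms picks its covariates by a stepwise method, so its p-values and intervals for arm are somewhat too optimistic; a short baseline list named in advance avoids this.

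*Combined protocol and SAP*

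**What the plan says.** Section 14 states that in the post-trial cohort "the relationship between outcomes (HbA1c and health care utilization) and study allocation will be examined" by linear and logistic regression, adjusting at once for several other covariates, "selected using a mixed purposeful / stepwise method". It lists no candidate variables and no entry or removal criteria. It names no covariate that must be kept, and no bootstrap or fixed-model sensitivity analysis. For the linear models it leaves open whether the outcome is analysed on the raw or the log scale.

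These models serve a stated aim. A secondary objective in Section 4 is "To evaluate the effectiveness of isCGM with CDE education and feedback on glycemic control at 24-52 weeks", which the same line describes as observational follow-up after the trial. Section 10 adds: "We will ascertain the effect of the intervention on HbA1c at 24 and 52 weeks, by review of NetCare". Section 17 concedes that this analysis "will no longer benefit from the expected confounder balance of randomization", because those with consent and a later HbA1c "will represent a non-random subset of those initially randomized". It does not mention the effect of covariate selection.

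The primary 12-week analysis, also in Section 14, fixes its covariates in advance: age and sex.

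**The concern.** When covariates are kept because they look useful in the same data, the final model's residual variance tends to be too small. Its standard error for arm also takes no account of other models that might have been chosen. The reported interval is then too narrow and the p-value too small, even when arm is forced into the model.

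At stake is the trial's only evidence on whether any benefit lasts, which Section 17 assigns to this follow-up. Two features add to the case for naming the model in advance. Section 6 states that analysts are not blinded to allocation. And nothing in Section 14 limits the candidates to baseline variables, while the follow-up form (Appendix 5.3) records medication changes, fingerstick testing and sensor use since baseline. These may lie on the path from intervention to HbA1c, and a stepwise rule could pick them up.

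**Working it through.** **The plan's own figure.** The only planning figure is the 12-week sample size. With difference 0.5, SD 0.78, two-sided 5% and 80% power, n per arm = 2(1.960 + 0.842)² × 0.78² / 0.5² = 38.2, so 39. The t-based calculation gives power 79.8% at 39 and 80.8% at 40, so the plan's 40 is right. With 20% loss, 80 / (1 − 0.20) = 100, as stated. None of this bears on the follow-up models, for which the plan gives no figure.

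**Inputs for the check.** The number with follow-up HbA1c, the candidate pool and the thresholds are not stated, so all are assumptions here. Appendix 5.2 lists more than 20 baseline items, which makes a pool of 20 possible but not certain.

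**Main simulation.** The true arm effect is zero. The outcome is 0.25 × each of three covariates plus standard normal noise; the other candidates are noise. Arm is always in the model, and the ordinary p-value and SE are read from the final model. The purposeful rule removes at p > 0.10 unless removal shifts the arm estimate by more than 20%. Type I error at nominal 5%:

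| n | Candidates | Backward, p-out 0.05 | Backward, p-out 0.20 | Purposeful | Fixed: all / none | True SD ÷ mean SE after selection |
|---|---|---|---|---|---|---|
| 80 | 10 | 6.9% | 7.2% | 6.9% | 5.4% / 5.3% | 1.05-1.08 |
| 50 | 10 | 5.9% | 7.1% | 6.3% | 4.3% / 4.5% | 1.04-1.12 |
| 80 | 20 | 7.7% | 8.4% | 8.5% | 5.1% / 4.7% | 1.08-1.16 |
| 50 | 20 | 8.3% | 10.8% | 9.5% | 4.5% / 4.5% | 1.09-1.25 |

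There were 3,000 replicates in the first row and 1,500 in the others. The Monte Carlo SE runs from √(0.05 × 0.95 / 3000) = 0.4 points to √(0.108 × 0.892 / 1500) = 0.8 points. In the worst cell the arm estimate had SD 0.337 against a mean reported SE of 0.269; 0.269 / 0.337 = 0.80, so the interval is about 20% too short.

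**Smaller pools and other rules.** A second set of runs forced in three covariates, one strongly prognostic, and used forward selection at p < 0.05 to 0.20. With 5 candidates it gave 5.6-6.1% at n = 60 and 5.0-5.6% at n = 80 (the n = 80 runs were cut short). At n = 60 it gave 6.6-7.3% with 10 candidates and 7.4-9.9% with 20. A third set, with backward selection at n = 60 to 80, gave about 5-7% with 5 candidates (no clear excess over fixed covariates), 6-6.5% with 10 and 8-12% with 20.

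**With imbalance between arms.** Section 17 expects balance to be lost. With an assumed shift of 0.3 SD on each of 20 covariates at n = 80, type I error was 15.7% unadjusted, 10.5-12.5% after selection and 4.8% with all 20 covariates fixed in advance. Stepwise adjustment removed part of the bias but still overstated certainty (SD ÷ SE 1.08 to 1.27).

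**Why a short list.** At n = 50, fixing all 20 covariates raised the SD of the arm estimate to 0.355, from 0.299 with none. A long fixed list keeps the error rate but loses precision.

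**The case against.** The strongest reply is that this is not a confirmatory analysis. Section 4 labels it observational, Section 10 puts it under its own heading outside the list of secondary outcomes, and Section 14 treats secondary outcomes as hypothesis-generating without multiplicity correction. No significance level is set for the cohort models themselves. A reader might infer that a promised error rate is broken; the documents make no such promise. What remains is that an exploratory interval should still have roughly its nominal coverage, and Section 17's caveats do not cover this defect.

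The second reply is that the inflation may be trivial. With 5 candidates it is, and the 20-candidate figures must not be read as the plan's own error rate. It is also fair that the method is only partly automatic, but the purposeful rule tried here was inflated as well (6.3-9.5%).

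Two further inferences are tempting and lack support. One is that selection would discard baseline HbA1c: a strong predictor is the least likely to be removed, and a strongly prognostic covariate was never dropped in the backward-selection runs that included one. The other is that the open choice of scale lets the analyst steer the HbA1c result: the clause covers utilization too, and may be there only for a skewed outcome.

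**Conclusion.** The point holds as a moderate one. Covariate selection makes inference on arm at 24-52 weeks somewhat too optimistic: type I error near 5% with 5 candidates, about 6-7% with 10 and about 8-12% with 20, against about 5% with fixed covariates. These ranges assume 50 to 80 participants, arm always in the model, and no systematic imbalance between arms. The direction is secure for pools of 10 or more; the size is unknown until the plan states its pool, thresholds and follow-up number. The primary 12-week conclusion is not touched.

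A reader might also infer that a fixed list would make the follow-up comparison unbiased. It would not. It restores the error rate lost to selecting covariates, but deals with the non-random follow-up only so far as the listed covariates capture it.

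**What to change.** Replace the stepwise clause in Section 14 with a short covariate list named in advance and limited to baseline variables:

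- For HbA1c: baseline HbA1c, age, sex and a few baseline factors that the investigators think relate to having a follow-up lab value. The documents do not show which factors these are, so the choice is a stated judgement.
- For utilization: the same list, with baseline utilization in place of baseline HbA1c.
- Arm in every model, the same list at 24 and 52 weeks, and one scale fixed for each outcome.
- Any stepwise model labelled exploratory. If its intervals are reported, use a bootstrap that repeats the whole selection.

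The cost is a sentence or two and no new data: Appendix 5.2 already collects demographics, diabetes history, medications and prior utilization, and Appendix 5.5 the baseline HbA1c. Some modelling flexibility is lost. The caveat in Section 17 on the non-random subset should stay.
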